11.3 Subgroup Analyses

Subgroups will be analyzed for the primary and secondary efficacy outcomes, including, but not limited to:

- a) Age
- b) Sex
- c) Body-mass index (BMI)
- d) Diabetes mellitus
- e) History of cardiovascular disease
- f) Baseline indication for antiplatelet therapy (i.e., eligible for 2nd randomization) (only for comparison of FDAC vs. SDPAC)
- g) D-dimer
- h) Need for mechanical ventilation at randomization
- i) High-sensitivity C-reactive protein (hsCRP)
- j) Prior history of VTE

Further details can be found in the Statistical Analysis Plan.

11.5 Sample Size Considerations

The sample size is based on the secondary analysis of the primary efficacy endpoint. With a 2-sided alpha of 0.05, a 40% event rate in the control arm rate in the group receiving both SDPAC and no AP therapy (estimated based on 3 recent case series of critically-ill patients with COVID-19),⁶⁻⁸ a 10% competing risk of mortality, and a 1% dropout rate (e.g., withdrawal of consent, loss-to-follow-up), approximately 750 patients should provide at least 170 events and therefore at least 80% power to detect a 35% relative risk reduction (RRR) for the FDAC vs. SDPAC comparison using Gray's test for equality of cumulative incidence function. The power for the AP therapy comparison is expected to be slightly less (~70%) as it is assumed that 10% of patients will not be eligible for the AP randomization. The approach of powering the trial based on the secondary analysis of the primary efficacy endpoint (i.e., cumulative incidence function) is expected to be conservative with respect to the primary analysis of the primary efficacy endpoint (i.e., unmatched win ratio), for which larger power is expected.

During the course of the trial, trial leadership will monitor the aggregate event rate and proportion of patients who proceed to the second randomization to ensure consistency with the initial assumptions and preserve the planned power for the trial. The target sample size may be increased to ensure accrual of an adequate number of efficacy endpoint events to preserve the overall initial planned power. Refer to the SAP for further details.

12. Data and Safety Monitoring and Review

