The primary analysis will be conducted by estimating the unmatched win ratio evaluating the composite in a hierarchical manner. A win ratio greater than 1 will be in favor of the FDAC arm and AP arm, respectively. In a secondary analysis of the primary composite endpoint, clinical event rates will be calculated using the time to first event according to the cumulative incidence function. Differences in clinical outcomes between the two treatment groups will be assessed using the Gray's test for equality of cumulative incidence functions.

With a 2-sided alpha of 0.05, a 40% event rate in the group receiving both SDPAC and no AP therapy at a median follow-up of 14 days, a 10% competing risk of mortality, and a 1% dropout rate, approximately 750 patients would provide approximately 170 events and therefore at least 80% power to detect a hazard ratio of 0.65 using Gray's test for equality of cumulative incidence function. This approach is expected to be conservative with respect to the primary efficacy analysis, for which greater power is expected using the win-ratio analysis.

3. Study Background & Rationale

In addition to respiratory insufficiency, patients with coronavirus disease (COVID)-19, the disease caused by the severe acute respiratory syndrome coronavirus-2 (SARS-CoV2), have a range of serious cardiovascular (CV) complications¹⁻⁴, including venous and arterial thrombotic events.⁵⁻⁸ Thrombotic event rates are believed to be substantially higher in patients requiring ICU-level care, among whom it is suggested that up to 2/3 may develop clinically evident or clinically silent venous thrombotic complications despite standard doses of thromboprophylaxis.⁶⁻⁸ While an accurate estimate of the rate of arterial thrombotic events is unknown at this time, case reports describe acute arterial thrombotic events, including ischemic strokes, acute coronary syndromes and ischemic limb events.^{5, 9, 10} Proposed mechanisms for the increased thrombotic risk in patients with COVID-19 include excessive inflammation and immobilization in the setting of aberrant coagulation parameters and diffuse intravascular coagulation (DIC).^{11, 12} In addition, early autopsy series have been notable for the presence of megakaryocytes in affected organs, suggesting that platelet aggregation and platelet-rich clot formation may be important pathogenetic mechanisms.¹³

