This is a phase 4, multicenter, open-label, 2x2 factorial, randomized-controlled trial using a PROBE design. The trial will be conducted in approximately 30 sites in the United States. Approximately 750 patients will be enrolled. Patients will be randomized in a 1:1 allocation ratio to receive either FDAC or SDPAC. In patients without an ongoing indication for AP therapy at baseline, a second randomization will be performed in a 1:1 allocation ratio to either AP or no AP therapy. Randomization to FDAC vs. SDPAC will be stratified by whether or not the patient is planned to receive non-study AP therapy and therefore would not qualify for randomization in the second factorial treatment comparison. Patients will be assessed clinically and with bilateral lower extremity venous ultrasound between 10 and 14 days post-randomization. Patients will be followed through hospital discharge or 28 days, whichever occurs first, for a maximum follow-up of 28 days. The anticipated total duration of the study is 6-12 months.

6. Study Population

Inclusion Criteria

Patients must meet all the following criteria to be eligible for enrollment:

1. Age \geq 18 years (male or female)
2. Acute infection with severe acute respiratory syndrome coronavirus 2 (SARS-CoV2)*
3. Currently admitted to an intensive care unit (ICU)**

**Acute SARS-CoV2 infection is defined as a documented, positive SARS-CoV2 RT-PCR, SARS-CoV2 IgM antibody test, or other accepted assay (see Manual of Site Operations) with active respiratory signs or symptoms during the current hospitalization.*

***Where ICU admission occurred \leq 96 hours prior to randomization. ICU admission also includes patients requiring ICU-level care in other units. Criteria for ICU-level of care are defined in the Protocol Appendix.*

Exclusion Criteria

Patients who meet any of the following criteria are excluded from the study:

1. Ongoing (>48 hours) or planned full-dose (therapeutic) anticoagulation for any indication
2. Ongoing or planned treatment with dual antiplatelet therapy
3. Contraindication to antithrombotic therapy or high risk of bleeding due to conditions including, but not limited to, any of the following:
 - a) History of intracranial hemorrhage, known CNS tumor or CNS vascular abnormality
 - b) Active or recent major bleeding within the past 30 days with untreated source
 - c) Platelet count $<$ 70,000 or known functional platelet disorder
 - d) Fibrinogen $<$ 200 mg/dL

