 - e) International normalized ratio (INR) $>$ 1.9
4. History of heparin-induced thrombocytopenia
5. Ischemic stroke within the past 2 weeks
6. Pregnancy
7. Study staff or their family members
8. Any condition which in the investigator's assessment might increase the risk to the patient or decrease the chance of obtaining satisfactory data to achieve the objectives of the study
9. Subjects for whom further care is being forgone at the decision of the subject, family, and/or treating team ("comfort measures only")

Exclusion-based laboratory results are based on most recent values from within 2 days prior to randomization for platelet count and INR and within 3 days prior to randomization for fibrinogen.

Patients who meet the following criterion are excluded from the second randomization (antiplatelet therapy vs. no antiplatelet therapy):

1. Ongoing or planned antiplatelet therapy, including aspirin monotherapy

7. Study Intervention

7.1 Investigational Product Information:

Acceptable initial regimens for FDAC include the following:

- UFH administered intravenously with a nomogram targeting an aPTT of 1.5-2.5 times the control as per institutional therapeutic target for treatment of VTE
- Enoxaparin 1 mg/kg administered subcutaneously every 12 hours (if CrCl \geq 30 ml/min)

Acceptable initial regimens for SDPAC include the following:

- Enoxaparin 40 mg administered subcutaneously once daily (if CrCl \geq 30 ml/min)*
- Enoxaparin 30 mg administered subcutaneously once daily (if CrCl $<$ 30 ml/min)
- Heparin 5,000 units administered subcutaneous three times daily

**Enoxaparin 30-40 mg administered SC twice daily may also be considered if CrCl \geq 30 ml/min and BMI \geq 35 kg/m².*

Acceptable regimen for randomized antiplatelet therapy is:

- Clopidogrel 300 mg administered once orally on the day of randomization, followed by 75 mg administered once daily on subsequent days

7.2 Randomized Treatment Assignment: Randomization to FDAC versus SDPAC and AP therapy versus no AP therapy will be done via an Interactive Web-based Randomization System (IWRS). Treatment will be open-label and hospital-supplied by the institutional pharmacy per standard practice using local, standard formulations, concentrations and titration.

Randomization and study treatment initiation should be done as soon as possible following ICU admission or the requirement for ICU-level of care and no longer than 96 hours after meeting ICU-level criteria.

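### The ~70% power given for the antiplatelet comparison does not follow from its one stated reason, 10% of patients ineligible, which gives about 75%

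*Combined protocol and SAP*

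**What the plan says.** Section 11.5 sizes the trial on the secondary (cumulative incidence) analysis of the primary endpoint. For full-dose versus standard-dose prophylactic anticoagulation (FDAC vs SDPAC), "approximately 750 patients should provide at least 170 events and therefore at least 80% power" to detect a 35% relative risk reduction. The Statistical Methods part of the synopsis expresses the same target as a hazard ratio and does not separate the two factorial comparisons: "approximately 750 patients would provide approximately 170 events and therefore at least 80% power to detect a hazard ratio of 0.65".

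Section 11.5 then turns to the AP comparison: "The power for the AP therapy comparison is expected to be slightly less (~70%) as it is assumed that 10% of patients" will not qualify for the second randomization. It prints no AP event count, no separate AP effect size and no second reason for the drop.

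Section 5 describes the second randomization: "In patients without an ongoing indication for AP therapy at baseline, a second randomization will be performed in a 1:1 allocation ratio". Section 6 identifies who is left out of it: "Ongoing or planned antiplatelet therapy, including aspirin monotherapy". Section 11.5 closes with "Refer to the SAP for further details", placed after its sentences on monitoring the event rate and possibly raising the sample size.

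**The concern.** The sentence presents ineligibility as the cause of a fall from 80% to about 70%. Power depends on the square root of the event count, so losing one tenth of the events should cost only a few points. A ten-point fall points either to a slip or to a further AP assumption that section 11.5 does not print: a larger ineligible share, a different event rate in ineligible patients, or a smaller effect.

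AP versus no AP is one of the trial's two primary comparisons. Section 11.5 also says that trial leadership will watch the share of patients entering the second randomization against the initial assumptions, and may enlarge the trial to protect planned power. The 10% share and the ~70% power are both natural reference points for that check, and they do not agree with each other.

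**Working it through.** **Inputs**
- Alpha 0.05, two-sided (section 11.5): "With a 2-sided alpha of 0.05, a 40% event rate in the control arm rate". The normal quantile is 1.960.
- 170 events in total from about 750 patients (section 11.5 and synopsis).
- Hazard ratio (HR) 0.65 (synopsis), matching the 35% reduction in 11.5. Using it for AP is an assumption, because 11.5 attaches the 35% to FDAC vs SDPAC only.
- 1:1 allocation in the AP randomization (section 5).
- 10% of patients ineligible (section 11.5). With similar event rates in eligible and ineligible patients, 0.9 × 170 = 153 events remain.

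**Formulas**, with d events and Φ the standard normal distribution function
- Schoenfeld: power = Φ(√d × |ln HR| / 2 − 1.960), where |ln 0.65| / 2 = 0.2154
- Freedman: power = Φ(√d × (1 − HR)/(1 + HR) − 1.960), where 0.35/1.65 = 0.2121

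**Step 1: the plan's FDAC figure, d = 170**
- Schoenfeld: Φ(13.038 × 0.2154 − 1.960) = Φ(0.848) = 80.2%
- Freedman: Φ(13.038 × 0.2121 − 1.960) = Φ(0.806) = 79.0%

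Schoenfeld reproduces the stated 170 events and 80%. Freedman falls one point short and serves as a sensitivity value.

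**Step 2: the AP figure, d = 153**
- Schoenfeld: Φ(12.369 × 0.2154 − 1.960) = Φ(0.704) = 75.9%
- Freedman: Φ(12.369 × 0.2121 − 1.960) = Φ(0.664) = 74.7%

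**Step 3: a check that needs no HR or event count.** This assumes only that the AP effect equals the FDAC effect. At exactly 80% power the expected test statistic is 1.960 + 0.842 = 2.802. With 90% of the events it is 2.802 × √0.9 = 2.658, and Φ(2.658 − 1.960) = 75.7%. The printed reason therefore explains 80 − 75.7 = 4.3 of the 10 points.

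**Step 4: variants that keep 10% ineligible**
- A further 1% loss of events (151.5 events): 75.5% (Schoenfeld) or 74.3% (Freedman).
- Different event rates in ineligible patients. Take illustrative cell rates of 40%, 26%, 26% and 16.9%, that is, a 35% reduction from each factor; the mean is 27.2%, so 675 eligible patients have 183.7 events.
  - If the 75 ineligible patients have the AP-treated rate (0.65 × 33% = 21.45%), they have 16.1 events. Eligible patients hold 91.9% of the total, or 156 of 170 events: 76.8% or 75.6% power.
  - If they have the no-AP rate (33%), they have 24.75 events. Eligible patients hold 88.1%, or 150 of 170: 75.1% or 73.8% power.

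**Step 5: what would give 70%**

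| Route | Schoenfeld | Freedman |
|---|---|---|
| Events needed at HR 0.65 | 133.0 (21.7% below 170) | 137.2 (19.3% below 170) |
| Event rate in ineligible patients relative to eligible ones, r | 2.50 | 2.15 |
| AP hazard ratio at 153 events | 0.669 | 0.665 |

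The second row solves 170 × 0.9/(0.9 + 0.1r) for the required events. Starting from exactly 80%, the required loss is 1 − (2.484/2.802)² = 21.4%, where 2.484 = 1.960 + 0.524. With 20% ineligible (136 events), power would be 71.0% or 69.6%.

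**The case against.** The strongest reply is that section 11.5 never says the AP effect is a 35% reduction. A slightly weaker AP effect closes the gap: at 153 events, a hazard ratio of 0.67 gives 69.7% (Schoenfeld) or 68.6% (Freedman). The planners may have had such a value in mind, and it may be printed in SAP text that is not part of the document reviewed. This stands as a limit on the finding: it cannot be said that ~70% is itself the slip. It does not rescue the sentence, which names ineligibility as the cause and gives no other.

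A second reply is that the figure is marked approximate. That does not cover the gap, since 75.7% does not round to 70%. A third is that ineligible patients might have more events. They would need 2.2 to 2.5 times the rate of eligible patients, and nothing in the document says so.

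It is also fair to say that little hangs on the figure. It understates AP power under the printed inputs, the sample size was set on FDAC vs SDPAC, and the plan expects the primary win ratio analysis to have more power. All of that stands, and it is why the point is minor.

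**Conclusion.** The sentence is wrong as written, in a limited sense: its stated reason does not yield its stated figure. Under 10% ineligibility, AP power is about 75% (75.9% Schoenfeld, 74.7% Freedman, 75.7% by scaling from exactly 80%), against ~70% printed. Because section 11.5 states 170 events and 80% as minimums, about 75% is also a minimum.

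The result assumes that 170 is the total event count, that the AP effect equals the FDAC effect (HR 0.65), that allocation is 1:1, and that event rates are similar in eligible and ineligible patients. Confidence in the arithmetic is high. Whether ~70% is a slip or rests on an unprinted assumption cannot be settled from the document. Severity is minor.

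**What to change.** In section 11.5, restate the AP power as about 75% under the stated 10% ineligibility. If ~70% was intended, keep it and state what produces it: the ineligible share, the event rate assumed in ineligible patients, or the AP effect size. The sponsor's statistician can tell which applies from the original calculation. Either way the change is one sentence, with no effect on the sample size, the design or the FDAC power.

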12.1 Data Collection

An electronic case record form (eCRF) will be used for data collection and query handling. The site investigator will ensure that data are recorded in the eCRF as specified in the study protocol and in accordance with the instructions provided. The investigator ensures the accuracy, completeness, and timeliness of the data recorded. The investigator will sign the completed eCRF. Data will be reviewed as defined in the Data Management Plan.

12.2 Safety Monitoring

As all study therapies have been approved for use in patients at risk for venous and arterial thrombotic events, this study has received an exemption from the need for an Investigational New Drug (IND). Investigators are required to report: (1) Serious Adverse Events Related to Study Drug, (2) Unexpected Problems, and (3) Adverse Events Leading to Drug Discontinuation.

1. Reporting of Serious Adverse Events Related to Study Drug

A serious adverse event (SAE) related to study drug must meet the following criteria:

- a) Be serious, meaning that in the view of either the local investigator or the TIMI Study group physician, the adverse event results in any of the following outcomes: death, a life-threatening adverse event, inpatient hospitalization or prolongation of existing hospitalization, persistent or significant incapacity or substantial disruption of the ability to conduct normal life functions, or a congenital anomaly/birth defect. Important medical events that may not result in death, be life-threatening, or require hospitalization may be considered serious when, based upon appropriate medical judgment, they may jeopardize the patient and may require medical or surgical intervention to prevent one of the outcomes listed in this definition.
- b) Be related to study drug, meaning that there is a reasonable possibility that the drug caused the adverse event. “Reasonable possibility” means there is evidence to suggest a causal relationship between the drug and the adverse event. In making this assessment, there should be consideration, based on the available information, of the probability of an alternative cause, the timing of the event with respect to study treatment, the response to withdrawal of the study treatment, and (where appropriate) the response to subsequent re-challenge.

Events that qualify as an SAE related to study drug and occur after the first dose of study drug has been administered (through the end of the study period), should be reported in the eCRF on the appropriate pages. SAEs related to study drug must be reported within 24 hours of knowledge of their occurrence. They should be clinically followed

until the event has resolved or stabilized. All confirmed SAEs related to study drug will be reported to relevant ethics committees, Institutional Review Boards, and investigators in an expedited manner in accordance with regulatory requirements.

2. Reporting of Unexpected Problems (UPs):

To qualify as a UP, an event must meet all of the following criteria:

- a) Be unexpected (in terms of nature, severity, or frequency) given (a) the research procedures that are described in the protocol-related documents, such as the IRB-approved research protocol and informed consent document; and (b) the characteristics of the subject population being studied.
- b) Be related or possibly related to participation in the research. “Possibly related” means there is a reasonable possibility that the incident, experience, or outcome may have been caused by the procedures involved in the research.
- c) Suggests that the research places subjects or others at a greater risk of harm (including physical, psychological, economic, or social harm) than was previously known or recognized.

3. Reporting of Adverse Events Leading to Drug Discontinuation: All adverse events (AEs) leading to investigational product discontinuation should be reported via the eCRF within 3 working days of knowledge of their occurrence.

4. Pregnancy: If any pregnancy is discovered during the course of the study, then investigators or other site personnel should contact the TIMI Hotline immediately but no later than 24 hours after knowledge of its occurrence. Investigational product should be discontinued immediately. The outcome of all pregnancies (spontaneous miscarriage, elective termination, ectopic pregnancy, normal birth or congenital abnormality) should be followed up (even if after trial completion) and documented on the paper Pregnancy Outcome Report form and sent to the TIMI Safety Desk.

12.3 Data Monitoring Committee (DMC)

An independent DMC will be appointed by the TIMI Study Group. The DMC will be responsible for safeguarding the interests of the patients in the study by assessing the efficacy and safety of the intervention during the trial, and for reviewing the overall conduct of the clinical trial. They will review overall safety in the trial and specifically the incidence of fatal or life-threatening bleeding. The DMC statistician will be able to have access to the individual treatment codes and will be able to merge these with the collected study data while the study is ongoing. The DMC Charter will be prepared to detail precise roles and responsibilities and procedures to ensure maintenance of the blinding and integrity of the study in the review of accumulating data.

12.4 Clinical Events Committee (CEC)

Suspected outcome events in the study including the components of the primary and key secondary efficacy and primary and secondary safety endpoints will be centrally adjudicated by an independent clinical events committee. Suspected outcome events in the study will be identified either by the site investigator or by electronic review of reported AEs. For all events identified for adjudication, the investigator will complete the appropriate modules of the eCRF and provide required source documentation.

13. Ethics and Dissemination

13.1 Ethical Conduct of the Study

This study will be conducted in compliance with Good Clinical Practice (GCP), including International Conference on Harmonization (ICH) Guidelines, and in general, consistent with the most recent version of the Declaration of Helsinki.

An Ethics Committee (EC) or Institutional Review Board (IRB) will approve the final study protocol, including the final version of the Informed Consent Form and any other written information and/or materials to be provided to patients.

Study personnel involved in conducting this trial will be qualified by education, training, and experience to perform their respective task(s). This trial will not use the services of study personnel where sanctions have been invoked or where there has been scientific misconduct or fraud (e.g., loss of medical licensure).

13.2 Protocol Amendments

Any change or addition to the protocol can only be made in a written protocol amendment that must be approved by the TIMI Study Group and the IRB prior to implementation.

